- i) 20 healthy adults, aged under 60 years old, recruited from the Toronto population at large.

Participants will participate in only one of the two samples (Experiments 2&4 or Experiment 6) . Recruitment for Experiment 4 was terminated on July 24 2018 due to technical issues

encountered with the equipment that could not be repaired by the manufacturer. We will recruit an equal number of male and female participants within each age-group. Participants of all ethnic and racial groups will be accepted, however adequate comprehension of the English language consent documents will be required.

The target age ranges for the age sub-groups have been selected based on our previous research, which suggests that significant age-related differences in tongue pressures in swallowing are detectable over the age of 60^[24-27]. Experiment 6 only includes healthy adults under 60 years of age at this time as this preliminary study exploring barium products/concentration and solids. The results will inform our decision to run a similar study in healthy older adults in the future.

Exclusion Criteria:

- The healthy adult participants for Experiments 2, 4, and 6 will be accepted into the study, provided that they have no prior history of swallowing, motor speech, gastro-esophageal or neurological difficulties, chronic sinusitis or taste disturbance.
- Individuals with a history of surgery to the speech or swallowing apparatus (other than routine tonsillectomy or adenoidectomy) will be excluded.
- Similarly, due to the requirement to swallow stimuli containing a significant carbohydrate load, individuals with Type 1 Diabetes will be excluded.
- For experiment 6, individuals who wear dentures will be excluded.
- Due to the fact that neurological impairments comprise an exclusion criterion, individuals with cognitive communication difficulties that may hinder comprehension of the study documents will be excluded from this study.
- For experiment 6, individuals with known allergies to medical adhesive will be excluded.
- Individuals with known allergies to ingredients of the food and liquid products used in the experiment will be excluded.
- As a further precaution due to the use of radiation in experiments 2 and 6, we will exclude women who report current pregnancy and individuals who report that they have had an x-ray to the neck in the past 6 months.

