- Finally, individuals who report that they are occupationally exposed to radiation will be advised that they should not participate if they believe their occupational radiation exposure may exceed half the allowed Ontario annual limit of 20 mSv.
- These exclusion criteria will be confirmed using a self-report questionnaire form at the time of intake into the study (see Appendix A). Any questions will be clarified through discussion with the research assistant responsible for participant intake, and, where necessary with the principal investigator.

Children will not be involved in this protocol due to the use of radiation.

Recruitment:

We will conduct a broad public advertising campaign through local newspapers, magazines, websites, mailings and posters at community centres, seniors' residences, places of worship, and around the University of Toronto and the University Health Network. In particular, for experiment 2, we anticipate advertising in a seniors' magazine (*50Plus*) and its associated website, which has been useful in previous studies. All participants in experiments 2 and 6 will be required to attend an intake appointment to confirm their eligibility to participate, introduce them to the research protocol, complete the intake questionnaire, and obtain informed consent.

Stimuli:

We have previously developed an array of stimuli in the target consistencies, defined using the International Dysphagia Diet Standardisation Initiative (IDDSI) testing methods (www.iddsi.org). Barium stimuli will be prepared using commercially available barium products (either E-Z-Paque® powdered barium, Polibar Plus liquid barium suspension, or E-Z-HD® powdered barium), prepared in either 20% or 40% w/v barium concentration. All stimuli will be prepared in the Swallowing Rehabilitation Research Laboratory not longer than 6 hours prior to scheduled use, according to a strict standard operating procedure. Barium stimuli will be transported to the radiology suite at Toronto General Hospital, as per routine clinical procedures.

Data to be collected from each participant during intake (Experiments 2 and 6):

The following types of data will be collected from participants in both Experiments 2 and 6:

- a) An intake questionnaire noting age, sex, ethnicity and race data and confirming eligibility based on the absence of reported exclusion criteria.

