Appendix A. Exclusion Criteria Questionnaire

This is a list of conditions that could alter the results of this research study, or impact your eligibility to participate.

Please read the list and let us know if any of these apply to you, so that we can be certain that you meet the requirements to participate in the study.

a) Medical or Occupational Conditions:

- People with a prior medical history of stroke
- People with a prior medical history of acquired brain injury
- People with a diagnosis of Parkinson's Disease
- People with a diagnosis of Multiple Sclerosis (MS)
- People with a diagnosis of Amyotrophic Lateral Sclerosis (ALS)
- People with a diagnosis of Huntingdon's Disease
- People who have slurred speech or facial muscle problems
- People who have a swallowing disorder
- People who have Type I (insulin-dependent) Diabetes
- People who have had surgery in the head and neck area (other than tonsillectomy or adenoidectomy)
- People who have had radiation to the head and neck for cancer
- People who experience extreme mouth sensitivity (for example, when you go to the dentist)
- People who wear dentures
- Women who are pregnant
- People who have allergies to barium or any of the food products used in the study
- People who have had an x-ray of their neck in the past 6 months
- People who work in a setting where they are exposed to radiation

b) Medication, Drug and Alcohol Use

- People who are taking sleeping pills or medication that makes them drowsy
- People who are taking "anti-Parkinson's" medications like Levodopa
- People who are experiencing dry mouth as a side effect of medication
- People who use drugs (Cocaine, Methamphetamine, Heroin, Ecstasy, etc.)
- People who are taking medicine that affects their sense of taste or smell

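### Appendix A, the form that is meant to confirm eligibility, has no item for three Section 4 exclusions (one of them adhesive allergy) and asks four others too narrowly

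*Combined protocol and SAP*

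**What the plan says.** Section 4 (Exclusion Criteria) accepts healthy adults only if they have "no prior history of swallowing, motor speech, gastro-esophageal or neurological difficulties, chronic sinusitis or taste disturbance". Further exclusions follow, including this one: "For experiment 6, individuals with known allergies to medical adhesive will be excluded". The list closes by naming the instrument that checks it: "These exclusion criteria will be confirmed using a self-report questionnaire form at the time of intake into the study (see Appendix A".

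Appendix A is that instrument. It has 22 items: 17 on medical or occupational conditions and 5 on medication, drug and alcohol use. Its single allergy item reads "People who have allergies to barium or any of the food products used in the study". On the history criteria it asks about "People who have a swallowing disorder", "People who have slurred speech or facial muscle problems" and six named neurological conditions. Its only item on taste is "People who are taking medicine that affects their sense of taste or smell".

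**The concern.** A protocol that names one form as the check on its exclusions needs an item on that form for each exclusion. Otherwise eligibility depends on participants volunteering what they were not asked, and nothing on the form records that the criterion was checked.

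Two things are at stake.

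- **Safety in Experiment 6.** The sponsor itself made known adhesive allergy an exclusion. In Session 6-1 electrode patches go over both masseter muscles and on the forehead. Session 6-2 repeats this and adds a metal scale marker taped to the face. A person with this allergy gets no prompt from the form beforehand.
- **Validity.** People with gastro-esophageal, sinus or taste problems, or with past swallowing, speech or neurological problems, could enter a sample described as healthy. Some of these conditions could plausibly affect the measured outcomes. The list under Data Processing includes breathing pattern, apnea duration and the time for the bolus tail to clear the upper esophageal sphincter.

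**Working it through.** The plan gives no figure to reproduce here. The check sets each Section 4 exclusion against the 22 items of Appendix A.

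| Section 4 exclusion | Appendix A | Result |
|---|---|---|
| Medical-adhesive allergy (Experiment 6) | The allergy item covers barium and foods only | No item |
| Gastro-esophageal difficulties | None | No item |
| Chronic sinusitis | None | No item |
| Swallowing, any past history | "People who have a swallowing disorder": present tense, and a disorder rather than difficulties | Narrower |
| Motor speech, any past history | "People who have slurred speech or facial muscle problems": present tense | Narrower |
| Neurological, any past history | Six conditions: stroke, acquired brain injury, Parkinson's, MS, ALS, Huntington's | Narrower |
| Taste disturbance, any cause | Only as an effect of a medicine being taken | Narrower |
| Allergy to food and liquid ingredients | Barium and food products; liquids not named | Arguable, not counted |
| Cognitive-communication difficulty | None | No item, not counted (see below) |
| Type 1 diabetes; pregnancy; neck x-ray within 6 months | Matching items | Equivalent |
| Surgery to the speech or swallowing apparatus; dentures (Experiment 6); occupational radiation | Head and neck surgery; dentures without the Experiment 6 limit; any occupational exposure | Broader |

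**Count.** Three exclusions have no item and four are asked more narrowly. Cognitive-communication difficulty is left out of the count because Section 9 requires confirmed understanding before the consent form is signed.

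**Is the present tense deliberate?** The form does ask about the past where it means to, as in "People with a prior medical history of stroke". The present-tense swallowing and speech items therefore differ in substance from Section 4. The motor speech item is the weakest of the four, because its facial-muscle wording adds some breadth.

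**Is text missing?** Appendix A runs unbroken to Appendix B with no redaction marked, so the absences belong to the form.

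**Do other intake steps close the gap?** None of those described shows an item on the missing conditions.
- The intake list of conditions in Section 4 is worded almost exactly like the opening line of Appendix A and appears to be the same form.
- Discussion with the research assistant is to clarify questions that arise. A person who was not asked about adhesive has little reason to raise it.
- The additional Session 6-1 questionnaire covers dental history.
- The risks in Section 5 do not mention skin reaction, and that list is addressed to Experiments 2 and 4.

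**Effect on the analysis.** Suppose an ineligible participant's measurements are shifted by δ.
- Between consistencies A and B within one person, (μ_A + δ) − (μ_B + δ) = μ_A − μ_B. The shift cancels if δ is the same for both consistencies. In Experiment 2 consistency is the within-participants factor, so that comparison is largely protected.
- Between age groups, with ineligible fractions p_old and p_young, the bias is δ(p_old − p_young). This does not cancel unless the fractions are equal. The documents give no value for δ or either fraction, so neither size nor direction can be stated.

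**Numbers affected.** Experiment 6: 20 planned. Experiment 2: the under-60 group of 40 is complete and the over-60 group of 40 is 90% complete, so 40 + 0.9 × 40 = 40 + 36 = 76 are enrolled and about 80 − 76 = 4 remain.

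**The case against.** The mismatch is hard to dispute. The better argument is that it matters little.

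- **Another form may exist.** The intake section describes a questionnaire that records age and sex and confirms eligibility. Appendix A has no age or sex field, so this could be a separate form whose items are not shown. The protocol does not append every form it uses; the dental history questionnaire is one example, so the short list of appendices proves little. This stands as a possibility, but the exclusion section still names Appendix A as the confirming form.
- **The allergy criterion covers known allergy.** Such a person is aware of it, reviews the protocol in Session 6-0 and receives written information before consenting. The consent pages are not in the reviewed copy and may mention adhesive. This lowers the likelihood of harm. It does not supply the missing prompt or the record that the question was asked.
- **Some narrower items are close calls.** The neurological reach is somewhat wider than six diagnoses, since the form also asks about slurred speech, facial muscle problems and anti-Parkinson's medication. The statement that medications are not a basis for exclusion does not exempt a taste disturbance caused by one. Both points are fair. There is still no general neurological item and no item on taste disturbance from other causes.
- **Recruitment is mostly done.** A new form would reach only about four more Experiment 2 participants. That is correct, so for Experiment 2 the remedy is mainly disclosure.

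**Conclusion.** The concern holds. Appendix A does not screen for three exclusions that Section 4 states and screens four more incompletely, so the claim that it confirms the criteria is wrong as written.

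The importance is moderate and rests mainly on the adhesive item, which concerns the 20 planned Experiment 6 participants. On their own, the other gaps would be minor. Experiment 2's consistency comparison is within participants and Experiment 6 is exploratory, so distortion of the results is probably small. The age-group comparison is more exposed, with no demonstrable direction of bias.

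The conclusion assumes that Appendix A is used as printed and that no form outside the reviewed documents asks about these conditions. The documents do not show which version of the form the enrolled Experiment 2 participants completed, so it is unknown whether any ineligible person was admitted.

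**What to change.** Bring Appendix A and Section 4 into agreement:

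1. Add items for medical-adhesive allergy (Experiment 6), gastro-esophageal difficulties, chronic sinusitis and taste disturbance of any cause.
2. Reword the swallowing, speech and neurological items to cover past history, and add a general neurological item beyond the six named conditions.
3. Mark each item as excluding or record-only, and for which experiment. This also settles two smaller ambiguities: the dentures item lacks its Experiment 6 limit, and the medication items are not shown as record-only.
4. If another intake form already covers the missing criteria, cite and append it. If the sponsor intends the narrower scope, amend Section 4 instead.
5. Report whether the roughly 76 Experiment 2 participants already enrolled were asked about the missing conditions.

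The cost is a one-page questionnaire amendment to the ethics board and one sentence in the report. No endpoint, sample size or analysis changes.

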- b) During the intake process, we will ask to review a list of conditions that could alter the results of the research study and identify whether any of these conditions apply. The disclosure of any medications that they are currently taking, allows us to control for the possible influence of medication on oral sensory and motor function. Medications do not qualify as the basis for exclusion. However, it is important for us to collect information regarding the use of benzodiazepines and neuroleptic medications that are known to have possible effects on swallowing, particularly with respect to causing xerostomia (dry mouth).

Data Collection Procedures:

Experiment 2: Prior to data collection, a nasal cannula will be placed around the participant's head with flexible prongs resting in their nostrils to measure airflow.

A single use disposable tongue bulb for the hand-held Iowa Oral Performance Instrument (IOPI) will be placed inside the participant's mouth. Tongue pressure signal will be collected at the anterior position during 3 anterior maximum presses and 3 saliva swallows.

[figure not shown]

Image 1. Tongue pressure sensors.

Following sensor attachment, the participants will be seated on a chair inside the fluoroscopy unit. The videofluoroscopy recordings of swallowing involve a pulse rate of 30 pulses per second and video capture at 30 frames per second. The video output line from the fluoroscopy unit and the nasal cannula will then be connected to the KayPENTAX Digital Swallow Workstation Swallowing Signals Lab equipment, which is located on a properly insulated cart with an uninterrupted power supply and isolation transformer.

Participants will be asked to swallow 27 boluses (i.e., 3 boluses each of 9 different barium stimuli) in videofluoroscopy, with concurrent measurement of nasal airflow. All barium stimuli in Experiment 2 will be prepared using E-Z-Paque® powdered barium, in a 20% w/v concentration. Videofluoroscopy will be performed at maximum temporal resolution (30 pulses/second) and captured at 30 frames/second. The order of stimulus presentation will follow a randomized block design. Participants will be allowed to take natural sized sips of each stimulus from cups containing 40 ml. Cup weights before and after each sip will be taken on a digital balance so that sip volume and mass can be calculated.

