Following sensor attachment, the participants will be seated on a chair inside the fluoroscopy unit. The videofluoroscopy recordings of swallowing involve a pulse rate of 30 pulses per second and video capture at 30 frames per second. The video output line from the fluoroscopy unit and the nasal cannula and sEMG sensors will then be connected to the KayPENTAX Digital Swallow Workstation Swallowing Signals Lab equipment, which is located on a properly insulated cart with an uninterrupted power supply and isolation transformer.

Participants will then be asked to swallow 22 different boluses, as follows: 1 thin bolus with a cued swallow, 12 boluses of thin barium prepared in either 20% or 40% w/v concentrations using different commercially available barium products (E-Z-Paque® powdered barium, Polibar Plus liquid barium suspension, and E-Z-HD® powdered barium), 3 boluses of mildly-thick barium (prepared with E-Z-Paque® powdered barium), and 6 solid stimuli, two each from IDDSI levels 5,

6 and 7 (minced & moist, soft & bite-sized and regular). The minced & moist and soft & bite-sized stimuli will be mixed with E-Z-Paque® barium powder. The regular stimulus will be a Carr's Table Water Cracker smeared with E-Z-Paque barium prepared in a paste consistency (IDDSI level 4). In addition to the swallowing tasks, five 3-second static recordings of the participant will be taken with the head in neutral (X2), chin up and chin down positions and during a voicing task (saying "ah"). Participants will also be asked to hold 1cc and 5cc water boluses in their mouth while the fluoroscopy is turned on to understand pharyngeal space. Task order will follow a randomized block design. For the liquid swallowing tasks, participants will be allowed to take natural sized sips of each stimulus from cups containing 40 ml. Similarly, for the solid food tasks, participants will be allowed to take natural sized bites or spoons-full from pre-portioned cups. Cup weights will be taken on a digital balance before and after each sip/bite will be taken on a digital balance so that bolus volume and mass can be calculated. Sips of water will be made available to participants between tasks, if desired.

Data Processing:

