We will model the impact of bolus consistency on measures of chewing and videofluoroscopic measures of pharyngeal bolus flow (i.e., the interval from the bolus passing the mandibular ramus until laryngeal vestibule closure; pharyngeal transit time) and pixel-based measures of post-swallow residue. The analysis will involve linear mixed model ANOVAs with repeated measures. A stepwise analysis approach will be used, first identifying relevant influences of tongue-pressure and nasal airflow patterns across stimuli. The influence of variations in bolus volume will also be explored using univariate tests, and, if confirmed to be significant, will be used as a covariate in the subsequent statistical models. Similarly, differences in the dependent variables as a function of sex or age (continuous or divided into groups) will be explored first in a univariate fashion, and, if significant, these between-participant factors will be included in the model.

For Experiment 2, **our main hypothesis is that liquids with similar gravity-flow properties will show similar pharyngeal bolus flow.** Our goal will be to detect differences in bolus flow measures ≥ 200 ms as a function of consistency, with a medium effect size (Cohen's $d \geq 0.5$)⁽⁹⁶⁾. We hypothesize that the healthy participants in these experiments will use higher amplitudes of tongue pressure and/or submental muscle contraction (sEMG) during oral propulsion of starch-thickened stimuli, thereby achieving a similar outcome for both starch- and gum-thickened liquids in terms of pharyngeal bolus flow. Model fit for different covariance structures will be explored using restricted log likelihood estimation. Age-group (< vs. > 60 years) will be used as a between-groups factor while bolus consistency will be used as the within-participants factor. Sample size calculations have been performed using the data from the PI's previous grant, in which ultrasound measures of the duration of hyoid movement differed by 200-400 ms between age-groups and tongue-pressure amplitudes varied by 10-35 mm Hg depending on the liquid studied. A power calculation shows that 36 participants per group will be needed to

detect this difference with 80% power ($\alpha=0.05$). Allowing a margin for attrition, we have therefore planned to enroll $n=40$ per participant group: total $N=80$ for Experiments 2 and 4. This sample size will also be adequately powered for Experiment 4 to detect differences ≥ 10 mm Hg in tongue-pressure amplitudes.

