- a) It is possible that participants may dislike the taste or texture of some of the stimuli in the study. Participants will be reminded that they are free to discontinue participation at any time.
- b) It is possible that participants may experience some fatigue during the data collection sessions. Participants will be reminded that they should disclose any fatigue or discomfort to the research team, and that they are free to discontinue any particular session or to withdraw from the study at any time.
- c) Participants will receive exposure to radiation during the videofluoroscopy. Based on a previous videofluoroscopic study that we have conducted in healthy adults, Experiment 2 is expected to involve 118+/-18 seconds of radiation exposure^[28], with an associated dose estimate of < 0.35 milliSieverts. Experiment 6 is expected to involve a maximum of 190 seconds of radiation exposure, with an associated dose estimate of < 0.5 millisieverts. We will terminate the protocol at the earliest opportunity following 3.5 minutes of exposure.
A dose of 0.5 mSv corresponds to a risk of 1 in 2,280,000 of developing a radiation-induced stochastic effect from a videofluoroscopy^[29], which is considered very rare. Background radiation exposure is known to occur in everyday activities such as flying a plane (0.005 mSv per hour) or smoking cigarettes (0.18 mSv per half pack) as well as during medical tests such as a chest x-ray (0.02 mSv) or a CT scan (10 mSv). According to Health Canada, the average Canadian experiences between 2 and 4 mSv background radiation exposure each year.
- d) Aspiration (entry of material into the airway) is a possible risk during the videofluoroscopic swallowing study that will be performed. This risk is always present for videofluoroscopic swallowing studies, which are intended to document the presence and severity of swallowing abnormalities, including (but not limited to aspiration). When aspiration is observed, standard procedures will be followed to encourage coughing and throat clearing to expel the aspirated material. The protocol will be terminated immediately. Any participant who experiences aspiration will be counseled regarding aspiration prevention strategies and aspiration-risk following the videofluoroscopy.
- e) Choking is an extremely unlikely event. However, in the event of choking, routine emergency procedures will be followed. All study personnel carry current CPR certification.

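### Bolus order is randomised in blocks, but no planned model has an order term, so any drift over the session misstates the standard errors, modestly

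*Combined protocol and SAP*

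**What the plan says.** Section 4, Data Collection Procedures, gives each Experiment 2 participant three boluses of each of nine barium stimuli, 27 in all, and states: "The order of stimulus presentation will follow a randomized block design". For Session 6-2 of Experiment 6 it says "Participants will then be asked to swallow 22 different boluses" and "Task order will follow a randomized block design". Neither place says what a block is.

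Section 4, Data Analysis, sets out the models: "The analysis will involve linear mixed model ANOVAs with repeated measures". For Experiment 2, age group is the between-participant factor, "while bolus consistency will be used as the within-participants factor". Sex and age enter if a univariate screen finds them significant. Bolus volume is treated likewise ("The influence of variations in bolus volume will also be explored using univariate tests"), and tongue pressure and nasal airflow are examined in a first step. Alternative covariance structures are to be compared by restricted likelihood. For Experiment 6, the terms carried forward are participant-level factors such as sex, height, neck measurements and occlusal pairs of teeth. No block, position, order or repetition term is listed for either experiment.

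Section 5, Risks, item (b), notes that "participants may experience some fatigue during the data collection sessions".

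**The concern.** The design controls presentation order, but the analysis does not use it. If transit times, residue or chewing measures shift as the session goes on, through fatigue, practice or adaptation to barium, that shift is a trend in the mean that no listed term can absorb. Comparing covariance structures does not fill the gap: none is named or tied to presentation order, and a covariance structure does not represent a mean trend shared by all participants.

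At stake is whether the standard errors and the level of the test of consistency are right. The answer depends on how blocks are built, so the undefined block is part of the problem.

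**Working it through.** The plan has no figure for an order effect to reproduce. Its only calculation (36 per age group, 80% power, 5% level) is not in dispute here and serves only to bound the SD.

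**Inputs from the protocol.** Experiment 2: 9 stimuli x 3 = 27 positions, 80 participants, target difference 200 ms, d = 0.5.

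**Assumptions, because the documents are silent.** Linear drift of D = 100, 200 or 400 ms from first to last bolus. Total SD 400 ms (200/0.5) or 299 ms (200/0.67, where 0.67 is the effect that a two-sided two-sample t-test detects with 80% power at 36 per group). Intraclass correlation (ICC) 0.3 to 0.7.

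**Step 1: variance due to drift.** Position variance is (27² − 1)/12 = 60.67, so drift variance is (D/26)² x 60.67. At D = 200 this is 59.17 x 60.67 = 3,590 ms².

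**Step 2: effect on the residual.** Within-participant variance is SD² x (1 − ICC). With SD 400 and ICC 0.5 it is 80,000 ms² (within-participant SD 283 ms). The increase is 3,590/80,000 = 4.5%, and √1.045 = 1.022, a 2.2% larger standard error. Across the range:

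| D (ms) | SD 400, ICC 0.3 | SD 400, ICC 0.5 | SD 299, ICC 0.7 |
|---|---|---|---|
| 100 | 0.4% | 0.6% | 1.7% |
| 200 | 1.6% | 2.2% | 6.5% |
| 400 | 6.2% | 8.6% | 24.0% |

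**Step 3: where the drift lies.**

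- *Three complete blocks of nine.* Between blocks: 9² x (3² − 1)/12 = 54.0. Within blocks: (9² − 1)/12 = 6.67. So 54.0/60.67 = 89% of the drift is common to all stimuli in a block and cancels from contrasts; 11% does not. The reported standard error carries all of it and is too large. A block factor cuts the excess residual variance at D = 200 from 4.5% to 0.5%.
- *Nine sets of three consecutive repeats.* Between sets: 3² x (9² − 1)/12 = 60.0. Within sets: (3² − 1)/12 = 0.67. So 60.0/60.67 = 99% is shared by the three repeats and does not average out over them, although a random-intercept model assumes that it does. At D = 200, SD 400 and ICC 0.5, the true variance per stimulus mean in a contrast, per participant, is 80,000/3 + 59.17 x 60 x 9/8 = 30,661 (9/8 because the nine slots are used without replacement). The model reports (80,000 + 3,590)/3 = 27,863. Since √(30,661/27,863) = 1.049, the true standard error is about 5% larger than the reported one.

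**Step 4: simulation.** 80 participants, 9 stimuli x 3 repeats, participant intercepts, within-participant SD 283 ms, 2,000 runs per cell, nominal level 0.05. Power is for a pairwise difference of 70 ms, chosen to give about 80% without drift.

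| Layout, D | Omnibus level, no order term | Pairwise level, no order term | Pairwise power, no order term | Pairwise power, block | Pairwise power, position |
|---|---|---|---|---|---|
| Complete, 200 | 0.043 | 0.048 | 0.77 | 0.78 | 0.79 |
| Complete, 400 | 0.018 | 0.030 | 0.71 | 0.76 | 0.77 |
| Consecutive, 200 | 0.079 | 0.060 | 0.75 | – | 0.77 |
| Consecutive, 400 | 0.178 | 0.094 | 0.69 | – | 0.78 |

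With linear position in the model, the pairwise level under consecutive repeats is 0.050 and 0.052. The Monte Carlo error at 0.05 is √(0.05 x 0.95/2000) = 0.005, so the 0.043 is not by itself distinguishable from 0.05; the 0.018 is.

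**Step 5: Session 6-2.** The boluses are 1 cued thin, 12 thin, 3 mildly thick and 2 of each of three solids: 1 + 12 + 3 + 6 = 22. Counts of 3 and 2 cannot be split into identical blocks that each contain every stimulus, so blocks by stimulus type are plausible. No size was computed for this session.

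**The case against.** The strongest reply is that the effect is small and hypothetical. The documents give no drift, no SD and no ICC. The fatigue remark is consent-risk wording, in a list introduced for Experiments 2 and 4, and does not predict drift in pharyngeal transit. The participants are healthy adults taking natural sips. With complete blocks and a 200 ms drift, simulated pairwise power is 0.77 without a block term and 0.78 with one. A short protocol that omits a nuisance term may be leaving out a detail rather than ruling it out, and Experiment 6 is expressly exploratory. All of this stands, and it limits the size. It does not supply the missing term.

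Three stronger readings are tempting, and the documents do not support them.

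- A reader might infer that position biases the stimulus comparisons, especially with 20 people in Experiment 6. Order is randomised, so stimulus means are unbiased on average; chance imbalance in position is part of ordinary sampling variation.
- A reader might infer that every consistency contrast loses real precision. With complete blocks of nine, only 11% of a linear drift lies within blocks, so it is mainly the reported standard error that is off.
- A reader might infer that a block factor belongs in every model. If blocks in Session 6-2 follow stimulus type, such a factor could be aliased with the food contrasts of interest.

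**Conclusion.** The point holds as a minor one. Order is randomised in blocks in Experiment 2 and Session 6-2, no listed model term represents order, and a drift common to participants would therefore go unmodelled. The consequence is misstated standard errors and test levels. Complete blocks of nine make the consistency test somewhat conservative, clearly so only at the larger drift. Consecutive repeats make a random-intercept analysis anticonservative, with an omnibus level of 0.079 at 200 ms.

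At a drift equal to the plan's own 200 ms target, the residual-based standard error rises by about 2 to 7%. That range rests on a linear drift, an SD of 299 to 400 ms and an ICC of 0.3 to 0.7, all assumed. A smaller drift would make the matter negligible: at 100 ms the rise is below 2% throughout.

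**What to change.** State what a block is in each experiment, keep the presentation position of every bolus in the analysis file, and add linear bolus position as a fixed effect in the Experiment 2 and Session 6-2 models, reporting its estimate with a confidence interval. Then, according to the layout:

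- Where each block is a complete set of all stimuli, a block factor may replace position.
- Where repeats of one stimulus are consecutive, keep position and add a participant-by-stimulus random effect.
- Where blocks are defined by stimulus type, do not fit a block factor; use position.

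The cost is a few sentences of analysis text and one to a few degrees of freedom. Position is already set by the randomisation, so no new data, swallows or radiation exposure are needed.
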